Furthermore, the impact on the result of social inequality will be thoroughly examined.

METHOD

Project design

This study is designed as a prospective registry-based observational study using modelled air/noise pollution data. The population is predominantly males from two Danish clinical trials (DANCAVAS and VIVA trials)

Study population

DANCAVAS I and II (41-43) are two similar population-based randomized, multicentered, clinically controlled studies designed to evaluate the benefits of 7-step multiple cardiovascular screening and modern vascular prophylaxis in a population of men and a small subpopulation of females, aged 60-74 years, living in the southern part of Denmark. For each participant, all relevant CVD risk factors were measured or determined.

The screening included (figure 1): 1) low-dose non-contrast CT scan to detect CAC and aortic/iliac aneurysms, 2) ankle-brachial blood pressure index (ABI) to detect peripheral arterial disease (PAD) and hypertension, 3) a telemetric assessment of the heart rhythm, and 4) a measurement of the cholesterol and plasma glucose levels.

The Viborg Vascular (VIVA) screening trial (44) is a randomized, multicentered, population-based clinically controlled study designed to evaluate the benefits of vascular screening and modern vascular prophylaxis in men between 65-74 years of age living in the region of Mid Denmark (Viborg County). For each participant, abdominal ultrasound scanning of the infrarenal aorta were performed to detect abdominal aortic aneurism (AAA), and ABI were measured to detect PAD and hypertension (45). In all, 18,749 men were screened.

A total of 33,723 participants in the age of 60-74 are included from the two cohorts. In both trials, an AAA was defined as maximal infrarenal diameter of 30 mm or more, and PAD was defined as an ABI < 0.90 or ≥ 1.40 using the same validated hand held Doppler-based methodology (46). We have accounted for traditional CVD confounders in all participants. This is unique for our study. Previous studies on air pollution and CVD burden have not been able to prospectively consider these confounding variables to the same extent.

Air pollution

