Primarily a multivariate Cox proportional hazards regression model will be used to examine the associations between air- and noise pollution and all-cause mortality and CVD morbidity and mortality when adjusting for inclusion date, sex, and other potential confounding factors at baseline.

Descriptive statistics of the main study variables to examine noise pollution will be presented in tables, frequencies with percentages of dichotomous/ordinal variables and medians with quartiles for numeric variables. Outcomes will be analyzed both as dichotomized variables, present CAC, severe CAC (CAC score above 400), AAA and PAD, and as the underlying continuous variables, CAC score, aortic diameter, and lowest measured ankle-brachial blood pressure index. Confounding CVD variables will be considered and adjusted for (e.g., lifestyle, medical history, QoL, weight,

height, waist circumference, blood pressure, ABI, calcium score for coronary arteries, aortic dimensions, HbA1c and lipid parameters).

To investigate hypothesis about noise we will, for each dichotomized outcome, estimate adjusted odds ratios using multivariable logistic regression, with cumulated noise pollution as exposure and the Framingham risk factors as confounders. The continuous variables will be analyzed in multivariable linear regression models and the cardiovascular risk factors as confounders.

To investigate the impact of work versus home address, we will compare regression models with accumulated air pollution from both work and home addresses with models with air pollution only from home addresses. ROC curves from both models will be compared to evaluate the hypothesis.

Ethics approval and consent

The DANCAVAS and VIVA studies were approved from “Videnskabsetisk Komité” (S20140028, S20160164 and M20080028). Access to the participants’ former residential addresses has been approved from “Sundhedsdatastyrelsen” (FSEID-00005213).

Feasibility

We have formed the group of researchers that will perform the study and we have received all the necessary approvals. The group includes professors in the areas where special skills are needed.

COLLABORATION

This project is a collaboration across disciplines and sectors (cardiology, physics, environmental sciences, surgery, public health). The study will be performed as a collaboration between:

- Cardiovascular Research Unit, Odense University Hospital - Svendborg; [name] and [name]

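### The Statistics section offers coronary calcium score, ABI and aortic dimensions as example confounders, although they are study outcomes and calcium is, on the protocol's own account, a likely step between air pollution and disease

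*Protocol*

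**What the plan says.** All of the following is in the protocol's METHOD section.

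- **Outcomes (Statistics).** The dichotomised and continuous outcomes are "present CAC, severe CAC (CAC score above 400), AAA and PAD, and as the underlying continuous variables, CAC score, aortic diameter, and lowest measured" ABI.
- **Confounders (Statistics, the next sentence).** "Confounding CVD variables will be considered and adjusted for", followed by an illustrative list that ends with "height, waist circumference, blood pressure, ABI, calcium score for coronary arteries, aortic dimensions, HbA1c and lipid parameters".
- **Primary Cox model (Statistics).** Mortality and CVD events are related to air and noise pollution "when adjusting for inclusion date, sex, and other potential confounding factors at baseline". Those other factors are not named there.
- **Noise models (Statistics).** The logistic models are fitted "with cumulated noise pollution as exposure and the Framingham risk factors as confounders". For the linear models: "The continuous variables will be analyzed in multivariable linear regression models and the cardiovascular risk factors as confounders".
- **Measurements (Study population).** DANCAVAS screening includes a "low-dose non-contrast CT scan to detect CAC and aortic/iliac aneurysms". For VIVA the text reads "For each participant, abdominal ultrasound scanning of the infrarenal aorta were performed to detect abdominal aortic aneurism (AAA), and ABI were measured". No CT is described for VIVA.

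**The concern.** A confounder is a cause, or a proxy for a cause, of both exposure and outcome. CAC, ABI and aortic size were measured once, at screening at age 60 to 74, after the accumulated exposure under study had largely occurred. They cannot have caused it. If exposure promotes atherosclerosis and atherosclerosis leads to events, a marker of atherosclerosis lies between the two, and adjusting for it removes that part of the effect.

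The Introduction sets out to determine the impact of lifetime exposure on CVD and mortality. Hypothesis 1 asks whether pollution is a risk factor after accounting for the traditional cardiovascular risk factors. A model that also holds CAC fixed answers a narrower question: the association that does not run through coronary calcification. Adjusting for CAC could also remove one of the two cohorts from the analysis.

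**Working it through.** **1. Is *confounder* consistent with the rest of the protocol?**

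- *CAC and air pollution: no.* The Introduction associates prolonged PM2.5 exposure with development of atherosclerosis. The Background says that long-term air pollution relates to CAC progression. It also describes CAC as subclinical coronary disease with prognostic value beyond the Framingham factors. Together these make CAC a candidate intermediate, and something other than a traditional risk factor.
- *ABI and aortic dimensions: inferred.* No section reports an effect of pollution on either. They are parallel signs of vascular disease and are outcomes of this study.
- *Noise: inferred.* The Background links noise to hypertension and to clinical events, but not to CAC.

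**2. Which models can the list reach?**

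| Model | Adjustment stated | Are the three markers excluded? |
|---|---|---|
| Cox, primary | inclusion date, sex, other baseline confounders | No |
| Logistic, noise | Framingham factors | Yes |
| Linear | cardiovascular risk factors, most naturally the same Framingham set | Not explicitly |

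The only list of confounders by name in the protocol is the one that contains the three markers, so it is the obvious source for the unnamed factors in the Cox model.

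**3. Direction of the effect on the estimate.** Let *d* be the log hazard ratio per SD of exposure that does not pass through CAC, *a* the change in CAC (in SD) per SD of exposure, and *b* the log hazard ratio per SD of CAC. Approximately:

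- without CAC in the model: log HR = d + a·b
- with CAC in the model: log HR = d

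The documents give none of *d*, *a* or *b*. Purely as an assumed range, take d = 0.05, a = 0.05 to 0.2 and b = 0.3 to 0.5:

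- low end: exp(0.05 + 0.05 × 0.3) = exp(0.065) = 1.067, against exp(0.05) = 1.051 with CAC
- high end: exp(0.05 + 0.2 × 0.5) = exp(0.15) = 1.162, against 1.051 with CAC

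This shows direction only. It is not an estimate for this study, and it assumes no unmeasured common cause of CAC and events.

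**4. Cohort loss if CAC is adjusted for.** Inputs from Study population: 33,723 participants in total and 18,749 men screened in VIVA.

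- Remaining: 33,723 − 18,749 = 14,974, and 14,974 / 33,723 = 44.4%
- Standard error ratio at equal event rates and exposure variance: √(33,723 / 14,974) = 1.50

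Sensitivity, changing one assumption at a time:

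- *Share of VIVA men in the total.* At 90%: 33,723 − 16,874 = 16,849 (50.0%), ratio 1.41. At 80%: 33,723 − 14,999 = 18,724 (55.5%), ratio 1.34.
- *DANCAVAS-to-VIVA event-rate ratio r.* The share of events kept is 14,974r / (14,974r + 18,749). At r = 0.5 it is 0.285, ratio 1.87. At r = 2 it is 0.615, ratio 1.28.

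In a model that accounts for cohort, information adds across cohorts, so dropping one cannot bring this ratio below 1. ABI and infrarenal aortic measurement are described for both trials, so this loss concerns CAC only.

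**The case against.** The strongest reply is that this is loose wording and not a planned error. The list is introduced as examples to be considered, it sits in the paragraph on noise, and no model is tied to it. A variable may properly be an outcome in one model and a covariate in another. Hypothesis 1 already states the intended adjustment as the traditional risk factors. The full Cox covariate list would normally be left to the SAP, so its absence from the protocol is not a fault.

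Most of this stands, and it rules out several stronger readings:

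- A reader might infer that the two roles are flatly incompatible, or that an outcome will be regressed on its own measurement. That would need both roles in one model. None is specified, and the noise logistic models exclude the three markers.
- A reader might infer that the primary Cox model will include CAC. The text does not say so; it only leaves the way open.
- A reader might infer that all three markers are intermediates for both exposures. The protocol supports this directly only for CAC and air pollution.

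One thing does not fall away. The protocol says that these variables are confounders and will be adjusted for. That is a positive statement, not a detail deferred to the SAP, and for CAC it contradicts the protocol's own account of the disease process. An SAP written from that list would carry the error into the primary analysis.

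**Conclusion.** The concern holds in limited form. Naming CAC as a confounder conflicts with the protocol's Introduction, Background and hypothesis 1. For ABI and aortic dimensions the objection is weaker: they are outcomes measured after exposure, and their place on the pathway is inferred. The analysis at risk is mainly the primary Cox model, possibly also the linear models.

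If CAC entered the Cox model, the estimated impact would probably be attenuated. The size cannot be derived from the documents, and none is claimed.

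The fall to 14,974 of 33,723 (44.4%), with a standard error about 1.5 times larger, is conditional and not a prediction. It requires that VIVA has no CAC measurement, that all 18,749 VIVA men are in the total, that the analysis is complete-case, and that event rates and exposure variance are equal in the two cohorts. It also presumes that the other covariates in the model are available in VIVA. Study population describes cholesterol and glucose only under DANCAVAS screening, but says that traditional confounders were accounted for in all participants.

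**What to change.** In the Statistics section, delete ABI, calcium score for coronary arteries and aortic dimensions from the list of confounders for the main association models, and leave the other listed covariates as they are. State that the three are outcomes. If a model adjusted for any of them is wanted, report it only as a secondary analysis, labelled *adjusted for subclinical disease*, with the number of participants it includes.

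The cost is a wording change before analysis. It needs no new data. If adjustment for these markers was never intended, nothing else in the plan changes.

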This study will provide more detailed data as we can model pollution levels hourly compared to the MESA Air's two-week periods. Furthermore, we will incorporate work addresses where previous studies are limited to home addresses only. The MESA Air study is the most comprehensive to date but limited as they divide the contributions into PM_{2.5} and NO_x only. Previous studies have provided air pollution data as an accumulated amount where we have the possibility to show if the air pollution is of local origin (e.g., traffic, wood stoves), national origin (e.g., power plants, industries, agriculture), or international origin (e.g., other countries, shipping). We can show which component contributes most and where the pollutant(s) comes from.

The American Journal of Hypertension released a call for clinical trials on the correlation between air pollution and CVD in 2018 (35), and a joint opinion was released in April 2021 by the World Heart Federation, American College of Cardiology, American Heart Association, and the European Society of Cardiology due to the increasing concern about air pollution in the development of cardiovascular disease (36). They state that *50% of the 6,7 million deaths that can be attributed to air pollution are due to CVD* (36), which is concerning due to the fact that the disease burden of air pollution seems to be “larger and higher-ranking” than some of the presently recognized CVD risk factors (37).

We published a method article in 2020 (38) accounting for the aims of our study and the release of the concerning joint opinion in Circulation has reinforced the importance of this study. Hence, this project will contribute with unique and precise data to show if a correlation between air pollution and CVD burden truly exists.

Another aspect of environmental risk factors is environmental noise. The first article about this subject was published in 1985, nevertheless, it is only in recent years we are seeing both growing quality and quantity of articles in esteemed

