journals about environmental noise. These articles unanimously report an increased risk of hypertension, coronary heart disease, stroke, heart failure and atrial fibrillation with even slightly increased levels of environmental noise (specifically road traffic noise and aircraft noise). One of these studies (39) was a cross-sectional study of residents in London who lived close to Heathrow Airport. The study found an increased relative risk for admission due to coronary heart disease and CVD. Another study relating to another cardiovascular complication, hypertension, found that long-term residential exposure to noise was associated with increased incidence of (self-reported) hypertension (40).

HYPOTHESIS

The purpose of this study is to determine the impact of individually accumulated exposure to air and noise pollution, as well as exposure fluctuations (peaks), on the incidence and prevalence of CVD. Noise pollution can be a significant confounder for the relation investigated and we will therefore include accumulated data for noise over time together with air pollution data.

The ICD or SKS disease classification code system will be used to identify clinical events for patients from the two trials (described below). CVD mortality and total mortality as well as clinical events from myocardial infarctions, percutaneous coronary interventions, coronary artery bypass grafts, heart failure, apoplexies, and bypass will be examined. The analysis will be stratified by socioeconomic status to determine if there is a social inequality in the air and noise pollution impact.

We will examine the individual air pollution exposure as well as noise exposure to understand each pollutants' contribution to the accumulated risk and demonstrate the impact of air and noise pollution on CVD morbidity and mortality. We hypothesize that:

1. the amount of accumulated air as well as noise pollution is a highly independent significant risk factor for clinical CVD, when accounting for all traditional cardiovascular risk factors.
2. certain subdivisions of the air pollution exposure carry the highest contribution for development of clinical CVD. This will provide novel and valuable information as this has never been investigated with the precision we can deliver.
3. accumulated air and noise pollution from both individual home addresses and work addresses together better predicts clinical CVD than models based solely on home addresses. No study has evaluated this before.

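### The noise models for CAC, AAA and PAD name no air-pollution term, so a noise estimate can partly reflect traffic air pollution at the same address

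*Protocol*

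**What the plan says.** The Statistics section makes a Cox model the primary analysis for mortality and cardiovascular morbidity and names air and noise pollution together there. For noise and the screening outcomes it specifies separate models:

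- Present CAC, severe CAC, AAA and PAD: "To investigate hypothesis about noise we will, for each dichotomized outcome, estimate adjusted odds ratios using multivariable logistic regression". The exposure and the adjustment set of these models are then given in these words: "with cumulated noise pollution as exposure and the Framingham risk factors as confounders".
- CAC score, aortic diameter and lowest ankle-brachial index: "The continuous variables will be analyzed in multivariable linear regression models and the cardiovascular risk factors as confounders".
- A general sentence in the same section: "Confounding CVD variables will be considered and adjusted for (e.g., lifestyle, medical history, QoL, weight", followed by further body measurements, blood pressure, imaging and laboratory values. The list is open, but every example is a personal or clinical characteristic.

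The Hypothesis section calls noise a possible "significant confounder for the relation investigated and we will therefore include accumulated data for noise over time together with air pollution data". It also aims to learn what each pollutant adds to the total risk, in a sentence that opens "We will examine the individual air pollution exposure as well as noise exposure to understand each". Its first hypothesis is that "the amount of accumulated air as well as noise pollution is a highly independent significant risk factor for clinical CVD", once traditional risk factors are accounted for.

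**The concern.** A variable confounds the noise estimate if it is correlated with noise and affects the outcome. The protocol supplies both conditions for air pollution.

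- **Correlation.** The Background section says the study can show whether "air pollution is of local origin (e.g., traffic, wood stoves" being its examples of local sources. The Noise pollution section computes noise from sources such as road transport, using traffic counts. Both exposures are modelled at the address. The reference list also includes a paper whose title concerns how traffic-related air pollution and noise are spatially related in two Danish cities; no coefficient is given.
- **Effect on the outcome.** The Background section reports that long-term air pollution relates to progression of CAC, and the study's own hypothesis is that air pollution raises cardiovascular risk.

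Framingham factors do not stand in for air pollution at the address. A noise model adjusted only for them can attribute part of an air effect to noise. In a cohort of this size, even a small shift of this kind can reach conventional significance and be reported as a finding about noise.

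**Working it through.** The protocol gives no figure to reproduce here, so the check is an illustration.

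**From the protocol.** 33,723 participants in total, of whom 18,749 men were screened in VIVA. CT for CAC is described only for DANCAVAS.

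**Assumed.** No true noise effect; air odds ratio (OR) 1.05 or 1.10 per SD; noise-air correlation ρ from 0.2 to 0.7; prevalence p of 3% or 10%; two-sided 0.05; noise modelled without error; other covariates unrelated to both exposures.

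**Step 1: shift in the noise estimate when air is omitted.** Shift in ln(OR) per SD = ρ × ln(OR of air).
- Lowest: 0.2 × ln(1.05) = 0.0098, OR 1.010.
- Highest: 0.7 × ln(1.10) = 0.0667, OR 1.069.

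In the linear models the shift has the same form, ρ × slope of air.

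**Step 2: standard error.** SE₀ = 1/√(n p (1−p)).
- p = 0.10: 1/√(33,723 × 0.09) = 0.0182.
- p = 0.03: 1/√(33,723 × 0.0291) = 0.0319.

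**Step 3: chance of p<0.05 for noise.** P(|Z + shift/SE₀| > 1.96), n = 33,723, p = 0.10:

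| Air OR per SD | ρ = 0.2 | ρ = 0.3 | ρ = 0.5 | ρ = 0.7 |
|---|---|---|---|---|
| 1.05 | 8.4% | 12.7% | 26.9% | 46.9% |
| 1.10 | 18.3% | 35.0% | 74.7% | 95.7% |

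At p = 0.03 the same grid runs from 6.1% to 55.2%.

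The full n suits AAA and PAD. For CAC, if all the VIVA men are in the total, n = 33,723 − 18,749 = 14,974. At an assumed 30% prevalence and ρ = 0.2 / 0.4 / 0.6, the chance is 8.5% / 19.4% / 37.5% (air OR 1.05) and 18.8% / 57.1% / 89.4% (air OR 1.10).

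**Step 4: after adding an air term.** With reliability R of the modelled air exposure (classical error), shift = ln(OR of air) × ρ(1−R)/(1−Rρ²) and SE = SE₀/√(1−Rρ²). At p = 0.10, over the same grid:
- R = 1: 5.0% throughout.
- R = 0.7: 5.3% to 27.5%.
- R = 0.5: 5.8% to 56.2%.

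**Step 5: simulation check.** 1,000 data sets per setting, n = 33,723, p = 0.10, outcome depending on air only:

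| Air OR, ρ | Noise only: formula | Noise only: simulated | With error-free air term | With air at R = 0.7 |
|---|---|---|---|---|
| 1.05, 0.2 | 8.4% | 8.1% | 5.0% | 4.6% |
| 1.05, 0.7 | 46.9% | 46.7% | 4.9% | 9.9% |
| 1.10, 0.2 | 18.3% | 19.7% | 4.5% | 6.5% |
| 1.10, 0.7 | 95.7% | 96.0% | 5.3% | 28.4% |

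With the error-free air term the mean noise OR is 1.00.

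**The case against.** The strongest reply is that nothing is contradicted. The Hypothesis section treats noise as the confounder and does not promise an air term in noise models. The first hypothesis concerns clinical CVD and independence from traditional risk factors, which a Framingham-adjusted noise model matches. If including noise together with air data means joint modelling throughout, the Statistics section merely fails to repeat it. The confounder list is open, and co-exposure models are often left to the SAP.

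Much of this is fair as a reading of the Hypothesis section: it does not specify the reverse adjustment, and the finding is better called an omission than a contradiction. But the Statistics section does state an adjustment set for these models, and an analyst following it would fit noise without air. The open list contains nothing of the kind. Such a model cannot show each pollutant's contribution, which is a stated aim.

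A second reply is that the size is hypothetical, the models are non-primary, and the remedy is incomplete. All of that stands. The inputs are assumed, the protocol states no significance level, and at the weakest inputs the effect is negligible. Nor is air pollution a single variable here: the protocol describes many species and components. The Statistics section does, however, already use accumulated air pollution as a model term when it compares home and work addresses. A noise-only estimate is also a legitimate quantity if labelled as such, which is why reporting both is preferable to replacing one with the other.

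**Conclusion.** The concern holds. As written, the logistic and linear noise models for CAC, AAA and PAD leave out a correlated exposure that the protocol itself expects to affect cardiovascular disease. Their estimates therefore cannot be read as effects of noise separate from air pollution.

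The likely shift is small in absolute terms, up to about 7% in the odds per SD under the assumed inputs. In a cohort of this size that could still turn a nominal 5% error rate into anything from little more than 5% to above 90%. The true value within that range cannot be known from the protocol.

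The point is limited to these non-primary models; the primary Cox result does not depend on them. It is worth correcting because the remedy is cheap. Confidence is medium, since the size rests entirely on assumptions.

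**What to change.** State in the Statistics section that accumulated air pollution enters each noise logistic and linear model, name the measure used, and report the noise estimate with and without it.

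This takes one sentence and no new data, because the exposure is already modelled for the study. The costs are:

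- **Wider noise intervals.** With one air term the SE grows by 1/√(1−ρ²): 2% / 5% / 15% / 40% at ρ = 0.2 / 0.3 / 0.5 / 0.7. With two air terms whose mutual correlation is 0.5 (assumed), it grows by 1/√(1−2ρ²/1.5): 3% / 7% / 22% / 70%. This favours keeping the air terms few.
- **Residual confounding.** Error in the modelled air exposure means the adjustment is partial. The two estimates should be read side by side, without treating the adjusted one as free of air pollution.

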Impact of Lifetime Exposure to Air and Noise Pollution on Cardiovascular Disease and Mortality - the AIRCARD Study.

NCT04353232

17/10/2023

Impact of Lifetime Exposure to Air and Noise Pollution on Cardiovascular Disease and Mortality - the AIRCARD Study.

INTRODUCTION

The purpose of this study is to determine the impact of individually lifetime accumulated exposure to air and noise pollution on the incidence and prevalence of cardiovascular diseases (CVD) and mortality.

Air as well as noise pollution have harmful effects on human health (1). Experimental and clinical studies have shown a strong impact between particulate matter (PM_{2.5}) and cardiovascular disease (CVD) (2, 3). Prolonged exposure to PM_{2.5} has been associated with the development of atherosclerosis and adverse cardiovascular events. However, also short-term exposure has been linked to acute coronary events (4, 5). PM_{2.5} is, however, a combination of many components of specific pollutants that have a size of two and a half microns or less in width. However, there is a knowledge gap, as investigation into which specific components of air pollutants that contribute the most to the development of CVD is lacking. There is a need to adopt and encourage preventive measures but also put in place environmental policies that are effective in promoting the reduction of exposure to pollutants. We want to aid in this shift by showing which specific pollutants contribute the most to the development of CVD so that we can better target these specific air pollutants for better prevention initiatives.

We will determine the contribution of sulfate, nitrate, ammonium, elemental carbon, organic carbon, silicon, or sodium ion, all contained in PM_{2.5}, to CVD. More relevant is that we can demonstrate which pollutants emitted from power plants, industries, and automobiles have the worst impact. We can provide insightful information to decision- and policymakers and this can help better target interventions against harmful pollution discharges and hereby significant prevention of many diseases with special emphasis on CVD and mortality.

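### Blood pressure at screening is adjusted for as a confounder, although the protocol reports that noise is associated with hypertension; no model is described for the total impact of exposure

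*Protocol*

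**What the plan says.** **Purpose.** The Introduction sets out to "determine the impact of individually lifetime accumulated exposure to air and noise pollution on the incidence and prevalence of cardiovascular diseases (CVD) and mortality". The Hypothesis section repeats this: "The purpose of this study is to determine the impact of individually accumulated exposure to air and noise pollution".

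**Hypothesis 1.** It is narrower. Accumulated air and noise exposure is expected to be a "highly independent significant risk factor for clinical CVD, when accounting for all traditional cardiovascular risk factors".

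**Noise and hypertension.** On the noise literature, the Background states: "These articles unanimously report an increased risk of hypertension, coronary heart disease, stroke, heart failure and atrial fibrillation with even slightly increased levels". It then cites a study in which "long-term residential exposure to noise was associated with increased incidence of (self-reported) hypertension".

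**Adjustment.** In the Statistics section, the logistic models for the dichotomised noise outcomes are to be fitted "with cumulated noise pollution as exposure and the Framingham risk factors as confounders". The linear models for the continuous outcomes also take cardiovascular risk factors as confounders. An open list of example confounders in the same section includes "height, waist circumference, blood pressure, ABI". The Cox model names date of inclusion and sex, and otherwise refers only to potential confounders at baseline.

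**Timing.** Under Study population, participants are aged 60-74 and hypertension is assessed at the screening visit.

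**The concern.** A confounder affects the outcome and is not itself produced by the exposure. Blood pressure at age 60-74 is recorded late in the exposure period, and the protocol reports evidence linking noise to hypertension. If that link is causal, blood pressure is a step between noise and disease. Adjusting for it then changes the quantity estimated, from the total effect of exposure to the effect given measured blood pressure.

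Both quantities are legitimate. The trouble is that the protocol describes a model for the second only, while its purpose reads as the first. The Introduction expects the results to inform planning of roads and buildings and legislation, where harm acting through raised blood pressure counts as harm. A weak or null adjusted noise estimate could be reported as no impact when part of the effect had been adjusted away.

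**Working it through.** The protocol gives no effect size, mediated share or power figure on this point, so there is nothing to reproduce. The check has two parts.

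**1. The text set side by side**

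- Is blood pressure adjusted for? Yes, by name in the open list. In the noise models it enters through the Framingham factors. The protocol does not enumerate these; on the usual definition they include blood pressure.
- Is it measured after exposure? It is measured at screening. Exposure is described as lifetime and accumulated. The window back to 1979 is stated for air pollution; no start year is given for noise.
- Does the protocol link noise to blood pressure? Yes, as an increased risk and an association with incident hypertension.
- Is a model without blood pressure described for the broader purpose? No.

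**2. Illustration of the mechanism (all effect inputs assumed)**

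Let *a* be the effect of noise on blood pressure (SD per SD), *b* the log odds of the outcome per SD of blood pressure, and *d* the direct log odds per SD of noise. Approximately:

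- total log odds ratio = d + ab
- log odds ratio adjusted for blood pressure = d
- share removed = ab / (d + ab)

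This was compared with simulated logistic models: n = 33,723 (the protocol's cohort size), 10 runs per scenario, outcome intercept -1.5, and one true confounder adjusted for in both models. Simulated shares are computed before rounding the odds ratios (OR).

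| a | b | d | ab / (d + ab) | OR without blood pressure | OR with blood pressure | Simulated share removed |
|---|---|---|---|---|---|---|
| 0 | 0.4 | 0.05 | 0 / 0.050 = 0% | 1.048 | 1.048 | about 0% |
| 0.05 | 0.2 | 0.05 | 0.010 / 0.060 = 17% | 1.064 | 1.054 | 16% |
| 0.10 | 0.4 | 0.05 | 0.040 / 0.090 = 44% | 1.089 | 1.048 | 44% |
| 0.20 | 0.4 | 0.05 | 0.080 / 0.130 = 62% | 1.135 | 1.050 | 62% |
| 0.20 | 0.4 | 0 | 0.080 / 0.080 = 100% | 1.082 | 1.000 | 99% |

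A simpler version assumes a total odds ratio of 1.10, so ln(1.10) = 0.0953. If 20% of the log effect runs through blood pressure, 0.0953 × 0.8 = 0.0762 and the adjusted odds ratio is 1.08. If 50% does, 0.0953 × 0.5 = 0.0477 and it is 1.05.

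Two limits apply. The simulation contains no unmeasured common cause of blood pressure and outcome, so it cannot test whether such a cause would change the direction. It also treats the measured blood pressure as the whole pathway, whereas a screening measurement would probably capture only part of it.

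**The case against.** The strongest reply is that the models match the hypothesis they serve. Hypothesis 1 covers noise as well as air and asks for an effect given all traditional risk factors, and the logistic models are introduced as the test of the noise hypothesis. The protocol never uses the term total effect, and it presents its control of traditional risk factors as a strength. This stands: the adjusted model should be kept. It does not settle the matter, because the stated purpose is not limited to the conditional effect.

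Several stronger readings are tempting, and the protocol does not support them:

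- *That the protocol says noise causes hypertension.* It reports increased risk and association. That blood pressure is on the pathway is a reasonable inference, not a statement of the protocol.
- *That no model without blood pressure is planned.* The list is open-ended, the Cox covariates are largely unnamed, and a statistical analysis plan that is not shown may contain staged models. One can say only that this protocol describes none.
- *That blood pressure follows decades of noise exposure.* For noise this rests on the words lifetime and accumulated alone.
- *That adjustment must bias towards no effect.* With an unmeasured common cause of blood pressure and outcome, conditioning on blood pressure can bias in either direction. Blood pressure may also stand in for unmeasured confounders, so a model without it is not free of bias either.

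The reply that all this belongs in the analysis plan carries less weight. The protocol itself names the adjustment variables and calls them confounders.

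**Conclusion.** The point holds in limited form. The protocol treats screening blood pressure as a confounder of an exposure that, by its own background, is associated with hypertension. The resulting estimates answer hypothesis 1 but not the broader purpose. If noise raises blood pressure and blood pressure raises the risk of the outcome, the adjusted estimate leaves out at least part of that pathway and will probably understate total impact.

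The size is unknown. The illustration runs from nothing removed to essentially all removed, depending entirely on assumed inputs, and residual confounding could change the direction. The documented pathway concerns noise; the protocol's background makes no matching statement linking air pollution to hypertension. The point does not show that the planned models are invalid or that a noise effect will be missed. It is a worthwhile and inexpensive improvement.

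**What to change.** In the Statistics section, add for each outcome a model adjusted for factors not plausibly caused by the exposure: age, sex, date of inclusion, socioeconomic status and smoking. Add the co-exposure too, that is, air pollution in the noise models and noise in the air models, because the Hypothesis section itself calls noise a possible confounder of the air pollution relation. Leave out baseline blood pressure and antihypertensive use. Report this model as the estimate of total impact.

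Keep the risk-factor-adjusted model for hypothesis 1 and label it as the effect conditional on measured risk factors. State that a null result from that model will not be read as no impact.

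The cost is one further model per outcome and two estimates to report and explain. It should need no new measurements: socioeconomic status is already planned for stratification. Smoking is not named in the protocol and is assumed here to fall under its lifestyle variables.
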